#### **Romidepsin Monotherapy**

As of 31 December 2008, a total of 781 subjects received at least one dose of romidepsin as monotherapy, including 353 subjects with hematologic malignancies and 428 subjects with solid tumors. The population of 428 subjects with solid tumors includes 26 pediatric subjects treated with romidepsin in NCI Study ADVL0212.

### **8.3 Agent Accountability**

Agent Inventory Records – The investigator, or a responsible party designated by the investigator, will maintain a careful record of the inventory and disposition of all agents received from appropriate parties.

## **9. Pharmacokinetic & Pharmacodynamic Studies**

### **9.1 Pharmacokinetic Studies**

The pharmacokinetic studies are noted on Figure 1.

### **9.2 Pharmacodynamic Studies**

The pharmacodynamic studies are noted on Figure 1.

#### **9.2.1 Biopsies (Optional)**

The patient will have the option of checking off boxes within the main consent form for this study to indicate consent or denial for the following optional studies.

A lymph node fine needle aspiration (FNA), core-needle biopsy or bone marrow biopsy will be performed prior to therapy and on between day 8 and 21 of cycle 1 after oral 5-azacitidine and romidepsin administration. Fine needle aspirations will be performed as follows:

**Fine Needle Aspirations (FNA):** A series of FNAs will be performed on palpable tumors in consenting patients as a function of drug exposure.

In general, at least 6 aspirations will be made using a sterile 10 cc syringe over the larger volume of the palpable tumor. Once the needle is placed into the tumor, the plunger will be withdrawn and pushed several times to obtain a sufficient sample from that location. Once withdrawn from the tumor, the syringe will be flushed clean in 1-2 mL of RPMI. This procedure will be repeated up to 6 times in one tumor, flushing the syringe needle in the same 1-2 mL of RPMI. Previous experiences in mice have established that performing fewer than 6 aspirations on any given tumor is associated with irreproducible results. Once the samples are acquired, the cells will be centrifuged, and resuspended in 1 mL of RPMI.

Correlations with the results of these studies will then be compared to the pharmacokinetic profile in order to establish the relationship with concentration, and the previous data obtained on the in vitro studies.

**Tumor Tissue Biopsies:** The biopsies will be performed by a surgeon if necessary, or by interventional radiology. A cytopathologist will evaluate the biopsy for tumor cells microscopically at the time of the biopsy. If multiple lymph nodes are available, the safest lymph node will be selected. The choice of FNA versus biopsy will be made based on safety, accessibility, and likelihood of being pathologic. A biopsy confirming recurrent or refractory disease is mandatory for participation in study. The second FNA or biopsy is encouraged, but is not mandatory. Correlative studies will be performed on de-identified tissue samples. Tissue will be labeled only with the protocol-specific unique identifier.

**Bone Marrow Biopsy:** a bone marrow aspirate and biopsy will be performed by the study team.

## 9.2.2

### Handling of Specimens

A frozen section will be performed to determine if there is lymphoma. Thereafter, biopsies may be snap-frozen or sent for tissue processing, and flagged for use in the protocol. Paraffin blocks will be made to confirm histological diagnosis, and appropriate immunohistochemical staining will be performed.

Remaining tissue will be used for the pharmacodynamic analysis.

## 10. STUDY CALENDAR

Baseline evaluations are to be conducted as indicated in the table below, prior to start of protocol therapy. Scans must be done  $\leq$ 4 weeks prior to the start of therapy. In the event that the patient's condition is deteriorating, laboratory evaluations should be repeated within 48 hours prior to initiation of the next

cycle of therapy.

Cycle	Screening	1				2- onward				End of treatment	End of Study (4 weeks after last dose)	Follow-up j
		Day 1	Day 8	Day 15	Day 22	Day 1	Day 8	Day 15	Day 22			
Eligibility & Safety Monitoring												
Informed Consent	X c											
Demographics	X c											
Medical History	X c											
Concurrent Medications	X f	X g	X	X	X	X	X	X	X	X	X	X
Physical exam	X f	X g	X	X	X	X				X	X	X
Vital Signs, weight	X f	X	X	X	X	X				X	X	X
Performance Status	X f	X	X	X	X	X				X	X	X
CBC w/ differential	X f	X g	X	X	X	X	X	X	X	X	X	X
Chemistries a, i	X f	X g				X				X	X	X
EKG	X c		X				X			X	X	
Toxicity Assessment			X	X	X	X				X	X	X
Serum β-hCG	X f											
Urinalysis	X c	X g										
Creatinine clearance	X											
Drug Dispensation												
Oral 5-azacitidine		X				X						
Romidepsin			X	X	X		X	X	X			
Efficacy Measurements												
CT (PET/CT optional)	X c						X b					
Brain MRI	X c, l											
Bone Marrow Biopsy k	X									X c		
Lymph Node Assessment	X c											
PK/Biomarkers												
Lymph Node Biopsy, FNA, or Bone Marrow Biopsy (Optional)	X c		X l									
PK		X d	X d			X						
Correlative Blood Sample		X h										

a) Chemistries include: Chem \*, Mg+, K+, Creatinine, Hepatic Function Panel (LFTs, bilirubin), and LDH. On romidepsin days of cycles 2 and onward, full chemistries may be drawn, but only K+ and Mg+ are required.  
b) CT to occur after cycle 2 and 6, Then CT q3-6 months, until disease progression or initiation of new therapy at the discretion of the Investigator. (PET/CT is optional)  
c) Bone Marrow biopsy will be required after cycle 2 for patients with bone marrow involvement at baseline who have a complete response by imaging and physical exam  
d) PK for Oral 5-azacitidine /Romidepsin: See figure 1 for details.  
e) To be done within 4 weeks of treatment start date  
f) To be done within 1 week of treatment start date  
g) Not necessary if conducted within 72 hours of screening assessment  
h) PD for Oral 5-azacitidine /Romidepsin: See figure 1 for details.  
i) Sodium, potassium, chloride, calcium, and glucose are part of the electrolyte assessment at every time point. Magnesium and phosphorous will be added to the electrolyte panel at Screening, and repeated before administration of romidepsin.  
j) Follow-up visits will be every 3 months for 1 year, or until the patient begins a new treatment for their disease for any patient that did not progressed on study.  
k) Based on clinical assessment  
l) For CNS disease only. Follow up MRI to be done at the discretion of the treating investigator.

**ALL SCHEDULED EVENTS +/- 3 DAYS**

## 11. MEASUREMENT OF EFFECT

The primary objective of this study is to evaluate the safety and tolerability of the study drugs. The measurement of toxicity is outlined in Section 7.

Although clinical response is not the primary endpoint of this trial, patients with measurable disease will be assessed by standard criteria. Patients will be re-evaluated at the end of even numbered cycles. Response will be evaluated with physical exam, computerized tomography (CT) and tissue biopsies as defined by the guidelines of the International Harmonization Project Group 2007 Revised Response Criteria. [1] Positron emission tomography / computerized tomography (PET/CT) will be utilized if available (optional). MM patients will be evaluated using criteria described in section 11.2.2

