#### **Treatment Plan (Phase II and Exploratory Cohort)**

Patients will be treated with oral 5-azacytidine and romidepsin at the MTD (i.e the Recommended Phase 2 Dose, or RP2D). The treatment will be administered as follows: oral 5-azacytidine 300 mg (flat dose) Days 1-14 and romidepsin 14 mg/m^2 on Days 8, 15, and 22 on an every 35 day cycle. .

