#### Tests

Safety evaluations on Day 1

Laboratory Evaluations Days 1, and each day of romidepsin

CT scans at the end of cycles 2 and 6. Then CT scans q3-6 months, until disease progression or initiation of new therapy.  
(PET/CT is optional)

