## **5.5 Duration of Follow Up**

Patients will have an end of study visit 4 weeks +/- 5 days after their last dose of drug to evaluate safety. Patients will be further followed every three months after the 4-week safety evaluation for one year, or until they begin a new treatment for their disease, for evaluation of delayed toxicity. Patients removed from study for unacceptable adverse events will be followed until resolution or stabilization of the adverse event.

For patients who have stable disease or better after 6 cycles of therapy, tumor assessment will be performed by medical history, physical, CBC with differential and chemistries every 3 months until progression of disease occurs. CT (PET/CT optional) will not be routinely used to monitor complete responses after 6 months, but rather, will be used when indicated, due to concern for disease progression.

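### Response-assessment schedules conflict, and the schema and calendar place no CT at the end of the four-cycle window that defines the Phase II primary endpoint

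*Combined protocol and SAP*

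**What the plan says.** Four places describe when disease is reassessed.

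- **Section 11, Measurement of Effect (introduction):** "Patients will be re-evaluated at the end of even numbered cycles". The next sentence gives the methods: "Response will be evaluated with physical exam, computerized tomography (CT) and tissue biopsies".
- **Synopsis, Schema Phase II and Exploratory Cohort, Future Cycles:** "CT scans at the end of cycles 2 and 6. Then CT scans q3-6 months, until disease progression or initiation of new therapy".
- **Section 10, Study Calendar, footnote b:** "CT to occur after cycle 2 and 6, Then CT q3-6 months, until disease progression or initiation of new therapy", followed by a clause leaving this to the investigator's discretion.
- **Section 5.5, Duration of Follow Up:** for patients with stable disease or better after six cycles, "tumor assessment will be performed by medical history, physical, CBC with differential and chemistries every 3 months until progression of disease occurs". In addition, "CT (PET/CT optional) will not be routinely used to monitor complete responses after 6 months"; it is used when progression is suspected.

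The Phase II regimen gives romidepsin "on Days 8, 15, and 22 on an every 35 day cycle", so one cycle is 35 days. Section 13.3 defines the Phase II and Exploratory Cohort response rate as the best response reached within four cycles. Section 13.2 stops the trial if two or fewer of the first nine patients respond, and drops the combination if nine or fewer of 24 respond. PFS and DOR are secondary objectives in Phase II and primary objectives in the Exploratory Cohort.

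**The concern.** The schedules agree at cycles 2 and 6 but not at cycle 4, nor after cycle 6. Cycle 4 is where the primary endpoint window closes. A site that follows the calendar scans once in the window, at its midpoint. A site that reads Section 11 as including CT scans twice, the second time at the window's end. A response that emerges on CT after the cycle 2 scan could then count in one patient and not in another within the same 24-patient arm, and the go/no-go decision rests on that count.

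PFS and DOR face the same problem in a milder form. Progression found by imaging is dated at the scan that shows it, so the recorded date depends partly on which section was followed. After cycle 6 the three-to-six-month range, the investigator's discretion and Section 5.5 widen the possible spread.

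**Working it through.** **1. The plan's own figures.** The two-stage design in Section 13.2 has 9 then 15 patients, null rate 25% and target rate 50%. With X ~ Bin(9, p) and Y ~ Bin(15, p), the probability of a positive result is the sum over x = 3 to 9 of P(X = x) × P(Y ≥ 10 − x).

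- p = 0.25: positive result 0.0485 (stated 0.049; the difference is immaterial); early stopping P(X ≤ 2) = 0.601 (stated 0.60); expected size 9 + 15 × (1 − 0.601) = 14.99 (stated 15).
- p = 0.50: power 0.805 (stated 80%).

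The design is correct as stated. The question is what the assessments feed into it.

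**2. Schedules in study days (35-day cycles).**

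| Source | Assessment days | CT in the four-cycle window |
|---|---|---|
| Section 11 (if CT is included) | 70, 140, 210, 280, 350, 420 | days 70 and 140 |
| Schema and calendar, 3-monthly later | 70, 210, 301, 393 | day 70 only |
| Schema and calendar, 6-monthly later | 70, 210, 393, 575 | day 70 only |

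The first divergence is at cycle 4: 210 − 140 = 70 days. The window of plus or minus 3 days on scheduled events cannot absorb it.

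**3. Primary endpoint.** Let f be the share of four-cycle responders whose response first shows on CT between days 70 and 140 and is not otherwise documented. If the true rate is 50%, the rate counted under the schema and calendar is 0.50 × (1 − f).

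| f (assumed) | Counted rate | Expected responders of 24 (10 needed) | Stopped at stage 1 | Power |
|---|---|---|---|---|
| 0 | 0.50 | 12.0 | 0.090 | 0.805 |
| 0.1 | 0.45 | 10.8 | 0.150 | 0.656 |
| 0.2 | 0.40 | 9.6 | 0.232 | 0.470 |
| 0.3 | 0.35 | 8.4 | 0.337 | 0.284 |

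The documents give no f for the combination. Section 7.2.2.4 reports a median time to response of 57 days for romidepsin alone in CTCL, with some responses at six months or later. Late responses therefore occur, but their share between days 70 and 140 is unknown.

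**4. Dating of progression.** Assume exponential PFS with true median m, so S(t) = 2^(−t/m), and all progression found at scheduled scans. Recorded PFS at day t is then S at the last scan on or before t, and the recorded median is the first scan day at or after m.

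- m = 120 days (assumed): S(70) = 0.667, S(140) = 0.445. Recorded median is 140 days under Section 11 and 210 under the calendar. Recorded PFS at day 182 is 45% against 67% (true 35%).
- m between 140 and 210 days: both record 210. Landmark rates still differ; at m = 180, S(140) = 58% against S(70) = 76% at day 182.
- m = 8 months: 9.2 months under Section 11; 9.9 (3-monthly) or 12.9 (6-monthly) under the calendar.
- m = 12 months: 13.8 months under Section 11 and 12.9 under either calendar version, so the order reverses.
- m = 120 days with half of progressions found clinically on the true date: under the calendar, ½ × 2^(−t/120) + ½ × 0.667 = ½ gives t = 190 days, against 140 under Section 11. PFS at day 182 is ½(0.349 + 0.667) = 51% against ½(0.349 + 0.445) = 40%.

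**The case against.** The strongest reply is that the calendar governs. The schema is headed for Phase II and the Exploratory Cohort and agrees with footnote b. The Section 11 introduction reads like Phase I or carried-over text: it names safety as the primary objective, says response is not the primary endpoint, and mentions MM patients, whom this trial does not enrol. That is a fair reading, but no text states it. Section 11.1 covers both phases, and Section 11 holds the only response criteria. Accepting the reply also does not help the primary endpoint, because the calendar is the version with no scan at cycle 4.

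A reader might infer that Section 11 already orders a CT at every even cycle. The documents do not support that firmly. The sentence on methods also lists tissue biopsies, and the calendar does not schedule those every two cycles. Re-evaluation at even cycles with CT only at cycles 2 and 6 is a possible reading.

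Physical examination takes place on Day 1 of every cycle, and Section 11.1.3 accepts superficial lesions as clinically measurable. Some responses and progressions, particularly in skin, will be documented without CT. This stands: it lowers f and shrinks the PFS differences. Section 11.1.3 nevertheless prefers imaging where both methods are used.

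Section 11.2.4 runs best response to progression without a cycle limit. Under that definition a cycle 6 scan would count. Section 13.3, however, sets the four-cycle limit in stating the primary objective.

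**Conclusion.** The conflict is real, is in current text, and should be corrected. Its main weight is on the primary endpoint: under the schema and calendar, the four-cycle window contains one scheduled CT and none at its close. Any missed responses push the count down, towards early stopping or a negative conclusion. The power figures show sensitivity and are not a forecast, since f is assumed and clinical documentation would reduce it.

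The effect on PFS and DOR is secondary. A reader might infer that the calendar inflates median PFS by 70 days. That holds only under scan-only detection with a true median of roughly 70 to 140 days. It vanishes for medians between 140 and 210 days, can reverse for longer ones, and is smaller when progression is found clinically. Nor can PFS dating alter the Phase II decision, because Section 13.2 uses response counts only and sets no PFS threshold or comparator.

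**What to change.** Reconcile the Phase II schema, Section 5.5, Section 10 footnote b and the Section 11 introduction into one efficacy-assessment schedule for all Phase II and Exploratory Cohort patients. It should:

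- include a response assessment with imaging at the end of cycle 4, so that the data match the window in Section 13.3;
- use one fixed interval after cycle 6 in place of the three-to-six-month range, and state whether it applies to complete responders, whom Section 5.5 now treats differently;
- date PFS and DOR events at the scan or examination that first documents them.

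The best-response definition in Section 11.2.4 should be aligned with Section 13.3 in the same amendment.

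The cost is amendment wording, at most one added CT for each patient still on study at cycle 4, possibly some further scans after cycle 6, and a possibly shorter recorded PFS. Treatment is unaffected.

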### 11.1 Evaluation of response:

For the phase I part of the study measurable disease will be utilized as the reference for response. For the phase II part of the study evaluable disease criteria will be utilized for response assessment.

#### 11.1.1 Definitions

Evaluable for toxicity. All patients will be evaluable for toxicity starting from Day 1 of Cycle 1.

Evaluable for objective response. Patients who have received at least one day of therapy, and have had their disease re-evaluated will be considered evaluable for response. These patients will have their response classified according to the definitions stated below. Patients who exhibit objective disease progression prior to the end of cycle 1 will also be considered.

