## Treatment Plan (Phase I)

Patients will be treated with oral 5-azacitidine and romidepsin administered as follows (detailed in Table 2): escalating oral 5-azacitidine from Days 1-14 (Dose cohorts -1 to 5) or Days 1-21 (Dose Cohort 6); and romidepsin administered intravenously on Days 8, 15 (Dose cohorts 1-4) of a 28 day cycle and Day 22 (Dose Cohorts 5 and 6) of a 35 day cycle. Cohorts of 3 patients will be enrolled sequentially as outlined in the dose escalation scheme

(Table 2). Once the MTD is reached the Phase II part of the protocol will be initiated in patients with T-Cell Lymphoma (Figure 2).

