**Table 3: Dose Escalation & De-Escalation Decision Rules:**

Number of Patients with DLT at a Given Dose Level	Escalation Decision Rule
0 out of 3	Enter 3 patients at the next dose level.
1 out of 3	Enter at least 3 more patients at this dose level. If 0 of these 3 additional patients experience DLT, proceed to the next dose level. If 1 or more of this group experience DLT, then dose escalation is stopped, and this dose is declared the maximally administered dose (MAD), and the dose level below is the MTD.
$\geq 2$	Dose escalation will be stopped. This dose level will be declared the maximally administered dose (highest dose administered).
$\leq 1$ out of 6 at highest dose level below the maximally administered dose	This is generally the recommended phase 2 dose. At least 6 patients must be entered at the recommended phase 2 dose.

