## **5.2 Dose-Limiting Toxicity**

A dose limiting toxicity (DLT) is defined as any toxicity not specifically included in section 5.2 that occurs within cycle 1 and is considered at least "possibly related to study drug administration." DLT is also defined as any toxicity possibly related to drug, occurring up to 7 days after completion of cycle 1 that results in a delay of initiating cycle 2. For patients who discontinue study drug administration after Cycle 1, DLT will be defined as any toxicity not specifically included in section 5.2 that occurs within 30 days of the last dose of drug on study, in cycle 1 that is considered at least possibly related to study

drug.

DLTs include:

- Hematologic dose-limiting toxicity will be defined as either Grade 4 neutropenia that does not resolve to  $\leq$  Grade 2 within  $\leq$  7 days, any Grade 4 thrombocytopenia, or any Grade 5 hematologic toxicity. At least three patients in each cohort must be evaluable for hematologic toxicity.
- Non-hematologic dose-limiting toxicity will be defined as any Grade 3, 4 or 5 non-hematologic toxicity, with the specific exception of:
- Grade 3 nausea or Grade 3 vomiting that in the opinion of the investigator occurs in the setting of inadequate compliance with supportive care measures specified in Section 5.1.7 and lasts for less than 48 hours.
- Grade 3 diarrhea that in the opinion of the Investigator occurs in the setting of inadequate compliance with supportive care measures specified in Section 5.1.7 and lasts for less than 48 hours.
- Grade 3 dehydration that, in the opinion of the investigator, occurs in the setting of inadequate compliance with supportive care measures specified in Section 5.1.7 and lasts for less than 48 hours.
- Grade 3 acidosis or alkalosis that responds to medical intervention by returning to  $\leq$  Grade 2 within 48 hours.
- Isolated (i.e. no other abnormalities) Grade 3 elevation of liver function tests (LFTs) without associated clinical symptoms, lasting for  $\leq$  5 days in duration.
- Isolated (i.e. no other abnormalities) Grade 3 elevation of amylase without associated clinical symptoms, lasting  $\leq$  5 days
- Grade 3 hypocalcemia, hypokalemia, hypomagnesemia, hyponatremia, or hypophosphatemia that responds to medical intervention.
- Grade 3 hypercholesterolemia.
- Grade 3 hypertriglyceridemia
- Grade 2 Alopecia
- Grade 3 Constipation
- Grade 3 Fatigue

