## **PTCL and other T-cell Lymphomas**

The activity of romidepsin was evaluated in a Phase 2, NCI-sponsored study in 48 subjects with PTCL or other T-cell lymphomas. Of these 48 subjects, 28 had PTCL and 20 had other T-cell lymphomas, including angioimmunoblastic, primary cutaneous large T-cell, gamma-delta T-cell, and anaplastic large T-cell lymphomas.

Among all 48 subjects, the ORR (CR+PR) was 31% (15/48). The CR and PR rates were 8% (4/48) and 23% (11/48), respectively. Fifteen percent (15%; 7/48) of subjects experienced stable disease. When response was evaluated among the 34 subjects who received  $\geq$ 2 cycles of therapy, the ORR was 44% (15/34) and the CR and PR rates were 12% (4/34) and 32% (7/34), respectively. Twenty-one percent (7/34) of subjects who received  $\geq$ 2 cycles of therapy experienced stable disease.

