## **13. STATISTICAL CONSIDERATIONS**

### **13.1 Study Design/ Primary Endpoints**

#### **Phase I**

This is an open label, single institution Phase I, 3-3 dose-escalation study. The primary objective is to determine the MTD of oral 5-azacitidine in combination with romidepsin. The safety and toxicity of this combination will be evaluated.

All patients who receive any amount of drug will be available for toxicity. Adverse events will be graded using the NCI CTCAE v4.0.

The dose escalation scheme will follow the guideline in Section 5.1.1.

Toxicities will be described by intensity at each dose level

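### Phase I has no DLT-evaluable set: any dosed patient is evaluable for toxicity, so someone who leaves cycle 1 without a DLT, even before romidepsin, can fill a slot in the 3+3 rule

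*Combined protocol and SAP*

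**What the plan says.** Two places define who is evaluable for toxicity. Section 11.1.1: "All patients will be evaluable for toxicity starting from Day 1 of Cycle 1". Section 13.1, under Phase I: "All patients who receive any amount of drug will be available for toxicity". Neither requires a minimum exposure or observation time.

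Section 5.2 ties a DLT to a toxicity "that occurs within cycle 1 and is considered at least" possibly related to study drug. Cycle 1 lasts 28 or 35 days, depending on the dose level (Table 2). Section 5.2 also has a clause for patients who stop ("For patients who discontinue study drug administration after Cycle 1, DLT will be defined as any toxicity"), with a 30-day window after the last dose, and one minimum: "At least three patients in each cohort must be evaluable for hematologic toxicity". It does not say what evaluable means there.

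Table 3 is worded in terms of entry. After 0 DLTs in 3 patients the instruction is "Enter 3 patients at the next dose level", and its last row sets a minimum of 6 entered at the recommended Phase II dose.

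Azacitidine starts on Day 1. The synopsis has "romidepsin administered intravenously on Days 8, 15 (Dose cohorts 1-4) of a 28 day cycle", and Table 2 gives Day 8 as the first romidepsin day at every level.

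Section 2.4.2 reports that 26 patients were enrolled in Phase I and that all were evaluable for toxicity. It does not say how many completed cycle 1.

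**The concern.** An any-dose set is the usual choice for adverse-event tables. It is not suited to a 3+3 decision, where each of the 3 or 6 patients is meant to show whether the combination causes a DLT during cycle 1. A patient who leaves in the first week has had azacitidine only. Under the stated definitions that patient is still evaluable, and under Table 3 still one of those entered. Nothing removes the patient from the denominator or calls for a replacement.

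Early exit is foreseeable. Section 11.1.1 itself provides for progression before the end of cycle 1, and Section 5.4 ends treatment at progression. Phase I patients had a median of 6.5 prior therapies (Section 2.4.2).

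DLT and MTD are Phase I primary objectives, and the MTD is the dose planned for 24 Phase II and 10 exploratory-cohort patients.

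**Working it through.** **The plan's own figures.** The documents give no operating characteristics for the 3+3 rule and no cycle 1 dropout rate. The nearest stated figure is the Phase I size of 36, maximum 45 (Section 13.2). It reproduces as 6 levels × 6 patients = 36, and 36 + 9 further patients at the MTD = 45. This arithmetic leaves no visible allowance for replacing unevaluable patients.

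**Escalation probability.** Under Table 3 a level is passed with 0 DLTs in 3 patients, or with 1 in 3 followed by 0 in 3 more. With true DLT rate p and q = 1 − p:

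P(escalate) = q³ + 3pq² × q³ = q³ + 3pq⁵

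**Adding unobserved leavers.** Suppose a share d of patients leaves cycle 1 without an observed DLT, for reasons unrelated to toxicity, and is counted as DLT-free. The effective rate is then p(1 − d). Both p and d are assumptions.

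At p = 0.40:
- d = 0: 0.60³ + 3(0.40)(0.60⁵) = 0.216 + 0.093 = 0.309
- d = 10%, effective rate 0.36: 0.262 + 0.116 = 0.378
- d = 20%, effective rate 0.32: 0.314 + 0.140 = 0.454

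At p = 0.33:
- d = 0: 0.301 + 0.134 = 0.434
- d = 10%, effective rate 0.297: 0.347 + 0.153 = 0.500
- d = 20%, effective rate 0.264: 0.399 + 0.171 = 0.570

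**A single leaver.** If exactly one of the first three patients is unobserved and counted as DLT-free, and all others are observed, P = q² + 2pq × q³. At p = 0.40 this is 0.360 + 0.104 = 0.464, against 0.309 with all observed.

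**Can the documents supply d?** Section 7.2.2.4 describes a romidepsin monotherapy study of 48 patients and then a subset: "When response was evaluated among the 34 subjects" who received at least two cycles. So (48 − 34)/48 = 29% did not. That group may include patients who completed cycle 1 and patients who stopped for toxicity, so 29% is at most a loose upper bound on d, not an estimate.

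**Why one or two patients matter at the MTD.** Section 2.4.2 numbers cohorts up to 7 and reports no toxicities at the MTD, but not that cohort's size. If each of the other six cohorts had at least 3 patients (an assumption), at most 26 − 18 = 8 were treated at the MTD. With no DLTs in n patients, the one-sided 95% upper bound on the DLT rate is 1 − 0.05^(1/n): 31% for n = 8 and 39% for n = 6.

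**The case against.** The strongest reply is that the two definitions describe an ordinary any-dose safety population. Section 13.1 moves straight on to adverse-event grading, and neither section says that this set is the Table 3 denominator. A reader might infer that the protocol scores early leavers as having no DLT. No passage says so; the documents are silent on how leavers are scored. That part of the reply stands. Silence still leaves the primary Phase I decision without a denominator rule, and the only definitions on offer would let these patients in.

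The second reply is that safeguards exist:
- **Three evaluable patients.** If any dose sufficed, the Section 5.2 clause would add almost nothing to cohorts of three, so it may intend something stricter. Three of the four DLTs in Section 2.4.2 were hematologic. But the clause is undefined, omits non-hematologic toxicity, and leaves up to 3 of 6 patients in an expanded cohort uncovered. Read through Section 11.1.1, it excludes nobody.
- **Follow-up after stopping.** The 30-day clause in Section 5.2 is muddled but may reach a patient whose last dose fell in cycle 1. Section 5.5 adds a visit 4 weeks after the last dose, and Section 7.6 captures new events for 30 days after withdrawal. A leaver is therefore not necessarily unobserved, and treating leavers as having no chance of an observed DLT may overstate the effect. Follow-up cannot, however, show the toxicity of romidepsin never given.
- **Leaving because of toxicity.** A patient who leaves with a qualifying related toxicity in cycle 1 is still a DLT. Only other leavers can dilute the fraction.

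The third reply is that no harm is shown. This stands. Escalation did stop, with 2 DLTs in cohort 7, and the statement that all 26 were evaluable is compatible with all having completed the window.

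**Conclusion.** The gap is real. The plan has no DLT-evaluable set and no replacement rule, its toxicity-evaluability definitions admit any dosed patient, and its dose rule counts patients entered. A patient who leaves cycle 1 for a non-toxicity reason, possibly before Day 8, can be counted as DLT-free, and that makes escalation more likely.

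The size is illustrative. With 10% or 20% unobserved leavers, the chance of escalating rises from 31% to 38% or 45% at a true 40% DLT rate, and from 43% to 50% or 57% at a true 33% rate. These figures assume that leaving is unrelated to toxicity, that leavers show no DLT, and that all of them are counted.

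A reader might go further and infer that the declared MTD is too high. The documents do not support that: Section 2.4.2 gives no cycle 1 completion figures, so bias in the actual MTD is neither shown nor excluded. The point should be acted on because existing records can settle it.

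**What to change.** In Sections 11.1.1 and 13.1:
- Keep the any-drug set for adverse-event tables.
- Define the DLT analysis set as patients who had a DLT, or who received both drugs and completed the cycle 1 DLT window.
- State that patients outside this set do not count toward the denominators of 3 and 6 in Table 3. In any further escalation, additional patients would then be needed to fill those places.
- Use the same definition for the evaluable-patient requirement in Section 5.2.

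For the completed Phase I, recount DLTs by cohort for the 26 patients from existing records. Report this beside the all-treated count, with the number per cohort outside the DLT set, and state whether the Table 3 minimum of 6 at the recommended dose is met.

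The cost is wording and a review of 26 records; no new data are needed. The downside is that some cohort denominators may become smaller, possibly at the recommended dose. The recount informs how firmly the MTD is supported and does not by itself call for a different dose.
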